Attachment 2. Protocol JBDA Clinical Laboratory Tests

Clinical Laboratory Tests

Hematology^b:

Hemoglobin
Hematocrit

Erythrocyte count (RBC)
Leukocytes (WBC)
Neutrophils
Lymphocytes
Monocytes

Eosinophils
Basophils
Platelets

aPTT
PT and PT/INR

Urinalysis^b:

Specific gravity
pH
Protein
Glucose
Ketones
Blood

Clinical Chemistry^a
Serum Concentrations of:

Sodium
Magnesium
Potassium
Total bilirubin
Alkaline phosphatase
Alanine aminotransferase
Aspartate aminotransferase
Gamma-glutamyl transpeptidase
Lactic dehydrogenase
Blood urea nitrogen
Creatinine
Uric acid
Calcium
Glucose, random
Albumin
Total protein
Chloride
Bicarbonate

Direct bilirubin^b, as needed
Creatinine clearance^b

Serum Pregnancy Test (females only)^b

Abbreviations: RBC = red blood cells; WBC = white blood cells; aPTT = activated partial thromboplastin time; PT = prothrombin time; PT/INR = international normalized ratio of prothrombin time.

^a Assayed by Lilly-designated central laboratory.

^b Local or investigator-designated laboratory.

Attachment 3. Protocol JBDA Hepatic Monitoring Tests for Treatment Emergent Abnormality

Selected tests may be obtained in the event of a treatment emergent hepatic abnormality and may be required in follow up with patients in consultation with the Lilly clinical research physician.

Hepatic Monitoring Tests

Hepatic Hematology^a

Hemoglobin
Hematocrit
RBC
WBC
Neutrophils, segmented
Lymphocytes
Monocytes
Eosinophils
Basophils
Platelets

Hepatic Chemistry^a

Total bilirubin
Direct bilirubin
Alkaline phosphatase
ALT
AST
GGT
CPK

Haptoglobin^a

Hepatic Coagulation^a

Prothrombin Time
Prothrombin Time /INR

Hepatic Serologies^{a,b}

Hepatitis A antibody, total
Hepatitis A antibody, IgM
Hepatitis B surface antigen
Hepatitis B surface antibody
Hepatitis B Core antibody
Hepatitis C antibody
Hepatitis E antibody, IgG
Hepatitis E antibody, IgM

Anti-nuclear antibody^a

Anti-smooth muscle antibody^a

Abbreviations: ALT = alanine aminotransferase; AST = aspartate aminotransferase; CPK = creatine phosphokinase; GGT = gamma glutamyl transferase; Ig = immunoglobulin; INR = International Normalised Ratio; RBC = red blood cells; WBC = white blood cells.

^a Assayed by Lilly-designated or local laboratory.

^b Reflex/confirmation dependent on regulatory requirements and/or testing availability.

Attachment 4. Protocol JBDA Pharmacokinetic and Exploratory Blood Plasma Sampling Schedule

Pharmacokinetic Sampling Schedule For Part A

Sample Number	Cycle	Day ^a	PK Sampling Time for LY3009120 ^b	Exploratory Blood Sample
1	1	1	predose	X ^c
2	1	1	0.5h	
3	1	1	1h	
4	1	1	2h	
5	1	1	4h	
6	1	1	6h	
7	1	1	8h	
8	1	1	10h	
9	1	2	Predose	
10	1	15	Predose	
11	1	15	0.5h	
12	1	15	1h	
13	1	15	2h	
14	1	15	4h	
15	1	15	6h	
16	1	15	8h	
17	1	15	10h	
18	1	28	Predose	X
19	1	28	0.5h	
20	1	28	1h	
21	1	28	2h	
22	1	28	4h	
23	1	28	6h	
24	1	28	8h	
25	1	28	10h	
26	2	1	Predose	

^a On Cycle 1 Day 1 in Part A only, the evening dose should be omitted to enable characterization of a full PK profile.

^b Predose PK samples should be collected prior to the morning dose, and all samples collected as close to the scheduled times as possible.

^c Baseline exploratory blood plasma sample (EDTA tube) can be collected ≤ 14 days before first dose of LY3009120, after eligibility is confirmed and at Cycle 1 Day 28 predose.

Pharmacokinetic Sampling Schedule For Patients in Part B

Sample Number	Cycle	Day	PK Sampling Time for LY3009120 ^a	Exploratory Blood Sample ^b	Urine Sampling (Part B only- up to 3 patients)
1	1	1	Predose	X	0 to 10h pooled samples (end time to coincide with PK blood draw)
2	1	1	0.5		
3	1	1	1		
4	1	1	2		
5	1	1	4		
6	1	1	6		
7	1	1	8		
8	1	15	predose		
9	1	22	predose	X	
10	2	28	predose	X	
11	3-n	28	predose	X	
12	Follow-up (Visit 801)	-	-	X	

^a Predose PK samples should be collected prior to the morning dose, and all samples collected as close to the scheduled times as possible.

^b Baseline exploratory blood plasma sample (EDTA tube) will be collected ≤ 14 days before first dose of LY3009120 after eligibility is confirmed. Samples will also be collected during treatment predose on Day 22 of Cycle 1, and Day 28 of each cycle thereafter; and during follow-up Visit 801. During treatment this sample will be collected for a maximum of 9 to 12 cycles.

Attachment 5. Protocol JBDA Recommendations for Reporting Serious Adverse Events

Recommendations for Reporting Serious Adverse Events

When contacting Lilly to report a SAE, please have the following information available:

Patient Demographics

- patient identification (number), sex, date of birth, origin, height, and weight

Study Identification

- full trial protocol number, investigator's name, investigator's number

Study Drug

- drug code or drug name, unit dose, total daily dose, frequency, route, start dose, cycle details, start date and last dose date (if applicable)

Adverse Event

- description, date of onset, severity, treatment (including hospitalization), action taken with respect to study drug, clinical significance, test and procedure results (if applicable)

Relationship to Study Drug & Protocol Procedures

Concomitant Drug Therapy

- indication, total daily dose, duration of treatment, start date, action taken

In Case of Death

- cause, autopsy finding (if available), date, relationship to study drug and protocol procedures.

Attachment 6. Protocol JBDA ECOG Performance Status

ECOG Performance Status

Activity Status	Description
0	Fully active, able to carry on all pre-disease performance without restriction
1	Restricted in physically strenuous activity but ambulatory and able to carry out performance of a light or sedentary nature, for example, light housework, office work
2	Ambulatory and capable of all selfcare but unable to carry out any work activities. Up and about more than 50% of waking hours
3	Capable of only limited selfcare, confined to bed or chair more than 50% of waking hours
4	Completely disabled. Cannot carry on any selfcare. Totally confined to bed or chair
5	Dead

Source: Oken et al. 1982.

Attachment 7. Protocol JBDA Creatinine Clearance Formula

Note: This formula is to be used for calculating CrCl from **local laboratory results only**.

*For serum creatinine
concentration in mg/dL:*

$$\text{CrCl} = \frac{(140 - \text{age}^a) \times (\text{wt}) \times 0.85 \text{ (if female), or } \times 1.0 \text{ (if male)}}{72 \times \text{serum creatinine (mg/dL)}} \text{ (mL/min)}$$

For serum creatinine concentration in $\mu\text{mol/L}$:

$$\text{CrCl} = \frac{(140 - \text{age}^a) \times (\text{wt}) \times 0.85 \text{ (if female), or } \times 1.0 \text{ (if male)}}{0.81 \times \text{serum creatinine (}\mu\text{mol/L)}} \text{ (mL/min)}$$

^a age in years, weight (wt) in kilograms.

Reference: Cockcroft and Gault 1976.

-OR-

$$\begin{aligned} \text{GFR(mL/min/1.73m}^2\text{)} &= 170 \times [\text{PCr}]^{-0.999} \times [\text{age}]^{-0.176} \\ &\times [0.762 \text{ if patient is female}] \times [1.18 \text{ if patient is black}] \\ &\times [\text{SUN}]^{-0.17} \times [\text{Alb}]^{+0.318} \end{aligned}$$

PCr= Plasma Creatinine, mg/dL; SUN= Serum urea nitrogen, mg/dL; Alb= Serum albumin, g/dL

Source: Murray and Ratain 2003

Attachment 8. Protocol JBDA Sampling Summary

This table summarizes the maximum number of samples and volumes for all sampling, and tests during the study. The summary below provides estimates. More samples could be required in the case of retests, additional health monitoring (if needed), or for patients continuing treatment beyond the protocol-specified number of cycles in the study. Fewer samples may actually be taken (for example, patients who discontinue from the study).

Protocol I6X-MC-JBDA Sampling Summary

Purpose	Sample Type	Maximum Amount per Sample	Maximum Number of Samples	Maximum Total Amount
Study qualification ^a	Blood	12 mL	1	12 mL
Health Monitoring (may be more than 1 tube) ^b	Blood	9 mL	11	99 mL
Drug concentration ^c	Blood	3 mL	26	78 mL
Pharmacogenetic stored sample	Blood	10 mL	1	10 mL
Tailoring biomarkers	Blood	10 mL	14	140 mL
PD samples ^d (Part A, designated expansion cohorts)	Tumor tissue		2 biopsies	2 biopsies
Other exploratory sample (Part B, all cohorts)	Tumor tissue		2 biopsies	2 biopsies
B-Raf status assessment biopsy ^f	Tumor tissue		1 biopsy	1 biopsy
Hepatic Monitoring ^e	Blood	3 - 30 mL	-	-
Total				Blood: 339 mL Tissue: 2 biopsies

^a Additional samples may be drawn if needed for safety purposes.

^b Total volume based on average number of 5 cycles.

^c Part A: 26 PK time points; Part B: 9 PK time points.

^d Only for patients in designated Part A expansion cohorts as noted in Section 8.2.4.1.

^e Based on laboratory safety values, unscheduled hepatic monitoring testing may be performed as part of patient follow-up, in consultation with the designated medical monitor.

^f Only for patients without historical B-Raf mutation test results or adequate archived tumor tissue sample available for genetic testing (Section 8.2.2).

Attachment 9. Protocol JBDA RECIST Criteria 1.1

Response and progression will be evaluated in this study using the international criteria proposed by the New Response Evaluation Criteria in Solid Tumors (RECIST): Revised RECIST Guideline (version 1.1; Eisenhauer et al. 2009).

CCI [REDACTED]

[REDACTED]

[REDACTED]

[REDACTED]

- [REDACTED]
- [REDACTED]
- [REDACTED]

[REDACTED]

[REDACTED]

[REDACTED]

- [REDACTED]
- [REDACTED]
- [REDACTED]

CCI [REDACTED]

[REDACTED]

[REDACTED]

[REDACTED]

[REDACTED]

[REDACTED]

[REDACTED]

[REDACTED]

[REDACTED]

[REDACTED]

[REDACTED]

[REDACTED]

[REDACTED]

[REDACTED]

CCI [REDACTED]

[REDACTED]

[REDACTED]

[REDACTED]

[REDACTED]

[REDACTED]

[REDACTED]

[REDACTED]

CCI [Redacted]

[Redacted]

[Redacted]

[Redacted]

[Redacted]

[Redacted]

[Redacted]

[Redacted]

[Redacted]

[Redacted]

[Redacted]

[Redacted]

[Redacted]

CCI
[Redacted text block]

[Redacted text block]

[Redacted text block]

[Redacted text block]

[Redacted]	[Redacted]	[Redacted]	[Redacted]
[Redacted]	[Redacted]	[Redacted]	[Redacted]

[Redacted text block]

CCI [Redacted]

[Redacted]	[Redacted]	[Redacted]
[Redacted]	[Redacted]	[Redacted]
[Redacted]	[Redacted]	[Redacted]
[Redacted]	[Redacted]	[Redacted]

[Redacted]

[Redacted]

[Redacted]

[Redacted]

[Redacted]

[Redacted]

[Redacted]

CCI [REDACTED]

[REDACTED]

[REDACTED]

[REDACTED]

[REDACTED]

[REDACTED]

Attachment 10. Protocol JBDA Toxicity Band Design

This section introduces the background of Toxicity Band design (Neuenschwander et al. 2008) and describes the key elements for this trial. Simulation results from the Toxicity Band design are presented. These results are also compared with those from the simulation of a traditional 3+3 design to demonstrate the benefit of implementing a Toxicity Band design in this trial. Fixed and Adaptive Clinical Trial Simulator (FACTS) software version 3.2 are used for all the simulations.

1.1 Introduction of CRM type approaches

The Continual Reassessment Method, and hereafter, CRM (O'Quigley et al. 1990) is the first Bayesian model-based approach developed for dose escalation studies. Compared to the traditional 3+3 design that only used current dose level DLT data to estimate the MTD, CRM utilizes prior dose toxicity information and all available DLT data to efficiently estimate the MTD. To improve the operating characteristics of CRM, Goodman et al. (1995), among others, have proposed modified- CRM (MCRM) procedures to make the model-based designs more acceptable in practice. The major modifications include:

- Always start at the lowest dose level.
- Limit the escalation increment.
- Escalate by cohorts rather than single patients.

Babb et al. (1998) proposed the Escalation with Overdose Control (EWOC) method that directly controls the probability of overdosing during dose escalation. EWOC is also a CRM-type method. During the escalation, EWOC selects the next dose such that the predicted probability that the new dose exceeds the MTD is equal to a pre-specified feasibility bound $\alpha = 0.25$. The connection between CRM and EWOC is that CRM typically uses the middle (mean, or median) of the MTD's posterior distribution as the next recommended dose, whereas EWOC uses the 25th percentile. Therefore, EWOC is a more conservative method than the original CRM method.

1.2 Toxicity Band design

All the aforementioned approaches use point estimates of the posterior distributions to recommend the next dose. Neuenschwander et al. (2008) extended the concept of EWOC and proposed to consider the uncertainty of the posterior distributions and use interval estimates to make the dose recommendation. We call their approach the Toxicity Band Design.

The Model

A two-parameter logistic model is used to model the relationship between dose and probability of a DLT:

$$\text{logit}\{p(d)\} = \alpha + \beta \log\left(\frac{d}{d^*}\right), \quad \beta > 0. \quad (1.1)$$

In the model, d is the true dose, $p(d)$ is the probability of a DLT at dose d . d^* is the reference dose such that α is interpreted as the log-odds of a DLT at d^* .

Toxicity Band

The probability of a DLT is categorized to four bands:

Under-dosing: $p(d)$ in $(0, 0.20]$

Targeted toxicity: $p(d)$ in $(0.20, 0.35]$

Excessive toxicity: $p(d)$ in $(0.35, 0.60]$

Unacceptable toxicity: $p(d)$ in $(0.60, 1.00]$

The over-dosing means $p(d) > 0.35$.

MTD Definition

The MTD is defined as a safe dose that has the highest probability of DLT in the targeted toxicity interval (20 to 35%). A safe dose means that the probability of DLT larger than 35% is below 25%.

Dose Recommendation

During the escalation, after each cohort of patients, we

- 1) Calculate the posterior probabilities of the four toxicity bands, for each dose.
- 2) Exclude the doses such that the posterior probabilities of over-dosing are larger than 0.25 (JBDA over-dosing control criteria). The remaining doses are the ones that satisfy the overdose control criteria.
- 3) Among the remaining doses, the dose with the highest posterior probability in the targeted toxicity band will be the model recommendation of the next dose.

In this study, the escalation will start from the lowest planned dose; the maximum dose increment is 100%; and each dose cohort will have a minimum of 3 patients enrolled to it. The Bayesian model-based toxicity band method that incorporates prior expectations about toxicity will be fitted to the data at the end of each cohort to recommend a dose for the next cohort. The investigators and Lilly CRP will consider both the model recommendation and the observed DLT rate at each cohort to determine the next dose level. Dose escalation will take into account PK and PD information when available. Additional patients may therefore be enrolled at a specific dose level to characterize PK/PD. Intermediate dose levels will be explored if deemed necessary after discussion between the sponsor and investigators.

1.3 Dose Ranges and Reference Dose

This study has eight pre-specified doses: 50, 100, 200, 300, 400, 500, 600 and 700 mg BID. The reference dose in model (1.1) is chosen as $d^* = 700$, the highest dose. The model typically has satisfactory performance by choosing the highest dose as the reference.

1.4 The Prior Distribution on Model Parameters

A Quantile-based uninformative prior (Neuenschwander et al. 2008) is used to derive a bivariate-normal prior on $(\alpha, \log\beta)$. This can be achieved by the following two steps: (1) derive a prior distribution of probability of DLT at each dose level (2) derive a bivariate-normal prior on $(\alpha, \log\beta)$ to match the distributions in the previous step.

Step 1

After discussing with CRP, PK and Toxicology scientists, we selected the median probability of DLT for the lowest dose 50 mg BID and highest dose 700 mg BID as 0.005 and 0.5, respectively, based on preclinical experience. The median probabilities of DLT of the intervening doses are calculated by assuming that the probabilities are linear in $\log(d/d^*)$ on the logit scale. We therefore obtain the prior median probability of DLT for each dose.

Table 1. Prior Median Probability of DLT at Each Dose Level

Dose Level	True Dose (mg, BID)	Median Probability of DLT
1	50	0.005
2	100	0.020
3	200	0.075
4	300	0.155
5	400	0.246
6	500	0.337
7	600	0.423
8	700	0.500

For each dose, the minimally informative unimodal Beta (a,b) distribution is derived as the prior distribution for the probability of DLT.

- For median Probability of DLT <0.5 , $b = 1$ and $a(<1)$ is tuned to match the median
- For median Probability of DLT >0.5 , $a = 1$ and $b(<1)$ is tuned to match the median

After obtaining the prior distribution of the probability of DLT, we calculate the 2.5% and 97.5% quantiles for each distribution. Figure 1 shows the three quantiles of each prior distribution.

[figure not shown]

Figure 1. Prior probability of DLT at each dose.

Step 2

Derive a bivariate normal distribution on $(\alpha, \log\beta)$ that stochastically gives the best fit to the 2.5%, 50%, and 97.5% quantiles of the prior probability of DLT at each dose. Figure 2 is the fitting generated by FACTS. The parameters $(\alpha, \log\beta)$ has a bivariate normal distribution with Mean = $(-0.092, 0.359)$, SD = $(2.507, 0.907)$, and $\rho=.282$.

[figure not shown]

Figure 2. The stochastic fitting for the prior on (, log)

1.5 Simulation Studies

We perform simulations under different scenarios to investigate the operational characteristics: Toxicity band method vs. traditional 3+3.

- 3-patient cohorts starting from the lowest dose. No dose skipping.
- Maximum number of patients: 33
- Stopping rules for Tox-band method: max sample size reached or the recommended next dose has been treated for 9 Patients:

We considered 8 scenarios to represent a wide range of possible curves. The true DLT rate of the MTD is fixed at 25% across scenarios. Scenario 1 and 2 are toxic cases that have MTD at the first and second level. Both scenario 3 and 4 (in blue color) have 300 mg at the MTD with either steep or flat curves. Similarly, we design scenario 5 and 6 to have the same MTD at 400 mg. Scenario 7 has MTD at 500 mg, whereas scenario 8 is a safe case that the MTD is at the last dose.

[figure not shown]

Figure 3. The Pre-specified probability of DLT under each scenario

Table 2. The Pre-specified probability of DLT under each scenario

	Pre-specified Prob. of DLT							
Dose	1	2	3	4	5	6	7	8
50	0.25	0.14	0.07	0.02	0.03	0.01	0.05	0.01
100	0.4	0.25	0.09	0.04	0.05	0.03	0.07	0.02
200	0.55	0.40	0.13	0.09	0.09	0.05	0.11	0.05
300	0.65	0.55	0.25	0.25	0.14	0.09	0.14	0.08
400	0.75	0.65	0.36	0.47	0.25	0.25	0.17	0.11
500	0.85	0.75	0.48	0.65	0.36	0.5	0.25	0.15
600	0.90	0.85	0.60	0.80	0.47	0.65	0.40	0.18
700	0.95	0.90	0.75	0.90	0.60	0.80	0.55	0.25

We ran 1000 simulations under each scenario to investigate the operating characteristics of the Toxicity Band and 3+3 methods. The results are summarized in Table 3 and 4.

Table 3. Probability of each dose selected as MTD, mean number of subjects, and mean percentages of a DLT under each scenario: Results based on 1000 simulations (Toxicity Band Method)

Dose	Scenarios							
	1	2	3	4	5	6	7	8
50	0.833	0.422	0.084	0.008	0.015	0.002	0.031	0
100	0.159	0.464	0.159	0.068	0.072	0.019	0.138	0.018
200	0.008	0.109	0.247	0.333	0.105	0.047	0.121	0.038
300	0	0.005	0.342	0.512	0.274	0.313	0.126	0.093
400	0	0	0.136	0.076	0.337	0.527	0.204	0.120
500	0	0	0.028	0.003	0.152	0.086	0.233	0.138
600	0	0	0.003	0	0.027	0.005	0.095	0.137
700	0	0	0.001	0	0.018	0.001	0.052	0.456
Mean # of Subj.	10.035	14.358	21.585	22.479	25.020	25.710	25.266	28.977
Mean % of a DLT	39.20	27.54	19.57	17.62	16.26	15.73	15.93	10.79

Table 4. Probability of each dose selected as MTD, mean number of subjects, and mean percentages of a DLT under each scenario: Results based on 1000 simulations (3+3 Method)

Dose	Scenarios							
	1	2	3	4	5	6	7	8
50	0.808	0.504	0.133	0.020	0.035	0.008	0.071	0.009
100	0.164	0.344	0.125	0.069	0.080	0.022	0.099	0.023
200	0.028	0.135	0.302	0.389	0.167	0.083	0.153	0.057
300	0	0.017	0.282	0.417	0.295	0.353	0.147	0.090
400	0	0	0.135	0.097	0.269	0.458	0.222	0.135
500	0	0	0.021	0.008	0.118	0.074	0.213	0.162
600	0	0	0.002	0	0.032	0.002	0.076	0.203
700	0	0	0	0	0.004	0	0.019	0.321
Mean # of Subj.	7.605	10.251	16.203	16.554	19.356	19.488	20.331	24.696
Mean % of a DLT	38.76	28.91	19.26	16.95	15.55	14.61	15.93	9.97

From the results, we can see that, in terms of MTD estimation accuracy, the Toxicity band method successfully identified the correct MTD with the highest selection percentages under each scenario, whereas 3+3 failed to identify the correct MTD with the highest selection percentages at half of the scenarios. The MTD determination based on 3+3 algorithm is generally one level lower than the true MTD. Moreover, in general, the Toxicity band method has a higher correct MTD selection percentage than the 3+3 design, under each scenario.

In terms of the mean number of subjects, the Toxicity band typically needed 4 to 6 more patients compared to the traditional 3+3. The mean percentages of a DLT are in general comparable across two methods, which indicates that the Toxicity band method is conservative and safe.

In sum, from the simulation studies, the Toxicity band method has a better MTD estimation accuracy, and a comparable safety profile, compared to the traditional 3+3 design.

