6.2. Summary of Study Design

Study JBDA is a multicenter, nonrandomized, open label, dose-escalation Phase 1 study of oral LY3009120 in patients with advanced or metastatic cancer. Patients will receive LY3009120 administered orally every 12 hours (BID) daily, in a 28-day cycle. LY3009120 will be administered as a flat dose. Study JBDA will consist of a dose-escalation phase in patients with advanced/metastatic cancer (Part A) followed by a dose-confirmation phase in advanced or metastatic melanoma carrying B-Raf or NRas mutations and NSCLC carrying KRas or B-Raf mutation (Part B).

The dose-escalation phase (Part A) ([Figure JBDA 6.1](#)), described in Section [7.2.2](#), will be guided primarily by safety assessments from Days 1 through 28 of Cycle 1 for patients in all cohorts. Dose escalation will occur until the maximum tolerated dose (MTD, defined in Section [7.2.2.1](#)) is determined. Patients will be enrolled in cohorts starting with the first dose level at 50 mg BID; dose levels of LY3009120 ranging from 50 to 700 mg BID may be evaluated. [Table JBDA 7.1](#) outlines the proposed dose-escalation scheme. The maximum dose increase that will be allowed is 100%. If the MTD has not yet been reached at the highest prespecified dose level, then additional dose levels may be investigated based on both safety and the available PK data. However, dose increments beyond 700 mg BID will never exceed a maximum increment of 33%. Patients in all cohorts will not be enrolled in the next cohort until safety from the previous cohort has been assessed. In Part A, the sample size is estimated to be approximately 30 to 35 patients depending on the relationship between exposure and toxicity as well as the relationship between exposure and pharmacodynamic effects.

After the last patient on Part A has completed Cycle 1 and the recommended dose for the dose-confirmation phase is determined, Part B will begin following an interim review of the data, as outlined in Section 10.9. The dose-confirmation phase will be opened in 3 cohorts of approximately 15 patients each, treated at a dose no greater than the MTD.

- Cohort A: Advanced unresectable/metastatic melanoma carrying a B-Raf V600X (where X represents any amino acid) mutation that has relapsed after treatment with B-Raf inhibitors, MEK inhibitors, or the combination of B-Raf/MEK inhibitors
- Cohort B: Advanced unresectable/metastatic melanoma carrying a NRas mutation

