7.2.2.2. Dose Escalation Method

[Table JBDA 7.1.](#) outlines the proposed dose-escalation scheme. In this study, the escalation will start from the lowest planned dose, the maximum allowed dose increment is 100%, and each new dose level will have a minimum of 3 patients enrolled to it. The Bayesian model-based toxicity band method (Neuenschwander et al 2008) that incorporates prior expectations about the dose-toxicity curve will be fitted to the data at the end of each cohort to recommend a dose for the next cohort. The toxicity band method is a Bayesian model-based design with built-in escalation with overdose control mechanism. After each cohort, the toxicity band model will utilize data from all available cohorts to make dose recommendation, based on the model based posterior probability of a DLT at each dose, and the overdose control criteria. The toxicity band method will stop if the pre-specified maximum number of subjects is reached or the recommended next dose has been taken by 9 patients.

During the escalation, the investigators and Lilly CRP will consider both the model recommendation and the observed DLT rate at each cohort to determine the next dose level and determine when to stop the escalation. Dose levels for each cohort will not exceed those recommended by the toxicity band model. Dose escalation will take into account PK and PD information when available. Additional patients may therefore be enrolled at a specific dose level to characterize PK/PD.

Intermediate or higher dose levels will be explored if deemed necessary after discussion between the sponsor and investigators. The JBDA toxicity band model has the ability to accommodate additional dose levels naturally.

Details regarding the JBDA toxicity band design are provided in [Attachment 10](#).

Table JBDA 7.1. Proposed Dose Escalation Scheme

Dose level	LY3009120 Dose (given BID) (mg)	Predicted Median AUC _{0-τ,ss} (ng*h/mL)	Predicted 5th and 95th percentiles AUC _{0-τ,ss} (ng*h/mL)	Predicted Median C _{max,ss} (ng/mL)	Predicted 5th and 95th percentiles C _{max,ss} (ng*h/mL)
1	50	1320	571-2560	139	63-250
2	100	2250	989-4550	232	108-442
3	200	2620	1150-5050	272	125-499
4	300	2770	1220-5310	290	140-528
5	400	3230	1440-6250	339	160-618
6	500	3780	1670-7460	393	187-750
7	600	3840	1630-7690	407	182-773
8	700	3980	1770-7780	419	201-771

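### Attachment 10 simulates escalation without dose skipping, but the written rule only caps each step at 100%, so Table 3 describes a stricter design than the one in the plan

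*Protocol*

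**What the plan says.** Attachment 10, section 1.5, lists among its simulation settings "3-patient cohorts starting from the lowest dose. No dose skipping". The ban on skipping appears nowhere else.

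The rules for running the trial state a different step limit:

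- Protocol 7.2.2.2, and SAP 5.3.2 in the same words: "the maximum allowed dose increment is 100%, and each new dose level will have a minimum of 3 patients enrolled to it".
- Attachment 10, section 1.2: "the maximum dose increment is 100%; and each dose cohort will have a minimum of 3 patients enrolled to it".
- Protocol 6.2 gives the same 100% maximum, with a 33% limit that applies only above 700 mg BID.

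Protocol 7.2.2.2 and SAP 5.3.2 send the reader to Attachment 10 for details, but the conduct paragraph there repeats only the cap. The model also sets a ceiling: "Dose levels for each cohort will not exceed those recommended by the toxicity band model".

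From Table 3, section 1.5 concludes that "the Toxicity band method successfully identified the correct MTD with the highest selection percentages under each scenario". It also concludes that the mean percentage with a DLT is comparable with 3+3, "which indicates that the Toxicity band method is conservative and safe", and that correct selection is generally higher than with 3+3.

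**The concern.** The planned doses are 50, 100, 200, 300, 400, 500, 600 and 700 mg BID. A doubling limit is the same as no skipping for the first two steps. From 200 mg the levels are 100 mg apart, so doubling can pass over one or two of them. If the model recommends such jumps, Table 3 shows the operating characteristics of a rule the trial is not bound to follow.

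Table 3 is the evidence for the accuracy and safety statements in section 1.5. Those statements were shown only for level-by-level escalation, and readers of a dose-escalation protocol rely on them when judging how many patients may be treated at doses that are too toxic.

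**Working it through.** **Inputs (Attachment 10).** Model: logit p(d) = α + β log(d/700). Prior: (α, log β) bivariate normal, means (−0.092, 0.359), SDs (2.507, 0.907), correlation 0.282. Doses with posterior P(p > 0.35) above 0.25 are excluded. The recommended dose is the remaining one with the highest posterior probability in (0.20, 0.35]. Cohorts of 3, maximum 33 patients, stop when the next dose already has 9. True DLT rates are from Table 2.

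**Assumption.** The plan does not say what happens when no dose passes overdose control. The reruns give 50 mg, because every column of Table 3 sums to 1.000.

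**Step 1: what the cap allows.**

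| Current dose (mg) | Next level (mg) | Highest planned dose within +100% (mg) | Levels that can be skipped |
|---|---|---|---|
| 50 | 100 | 100 | 0 |
| 100 | 200 | 200 | 0 |
| 200 | 300 | 400 | 1 |
| 300 | 400 | 600 | 2 |
| 400 | 500 | 700 | 2 |
| 500 | 600 | 700 | 1 |

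**Step 2: does overdose control prevent the jumps?** After 0/3 at 50, 100 and 200 mg the model recommends 500 mg. The cap reduces this to 400 mg, where the overdose probability is 0.13; no-skip gives 300 mg. After 0/3 at 400 mg as well, the overdose probability is 0.165 at 600 mg and 0.247 at 700 mg, against the 0.25 limit. The next dose is then 700 mg, or 600 mg on a coarse integration grid that gives 0.250 at 700 mg. Either one skips a level.

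**Step 3: reproduce Table 3 without skipping, then change only the step rule.** There were 20,000 trials per scenario and rule, and ranges cover different numerical integrations. Scenarios 1 and 2 are left out because skips occur in only about 1% and 8 to 9% of trials.

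| Scenario | Mean N: Table 3 | no-skip | cap | Mean % DLT: Table 3 | no-skip | cap | Table 4 (3+3) |
|---|---|---|---|---|---|---|---|
| 3 | 21.6 | 21.8 | 22.5 | 19.57 | 18.4 | 19.7 | 19.26 |
| 4 | 22.5 | 22.5 | 23.4 | 17.62 | 17.6 | 19.3 | 16.95 |
| 5 | 25.0 | 24.9–25.0 | 25.2 | 16.26 | 16.1 | 17.8 | 15.55 |
| 6 | 25.7 | 25.5 | 25.3 | 15.73 | 15.8–15.9 | 17.5 | 14.61 |
| 7 | 25.3 | 25.2 | 25.1 | 15.93 | 15.8–15.9 | 17.3 | 15.93 |
| 8 | 29.0 | 28.9–29.0 | 26.6 | 10.79 | 11.1 | 11.7 | 9.97 |

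(The cap columns show one integration.) The no-skip reruns match the printed mean N. The cap misses it in scenario 8 (26.6 against 29.0), so Table 3 does describe no-skip. The one clear miss in mean % DLT is scenario 3 (18.4 against 19.57).

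**Step 4: effect of the written rule.**

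| Scenario | Trials with a skip | Rise in mean % DLT (points) | Mean patients at true DLT rate > 35%: no-skip → cap | Correct MTD selected: no-skip → cap |
|---|---|---|---|---|
| 3 | 55% | 1.3–1.4 | 3.7 → 5.1 | 34% → 30–31% |
| 4 | 71–72% | 1.7 | 3.3 → 4.8 | 53% → 46–47% |
| 5 | 76% | 1.7–1.9 | 3.7 → 4.5–4.7 | 32–33% → 37–38% |
| 6 | 88–89% | 1.6–1.9 | 3.2 → 3.3–3.6 | 53% → 57–58% |
| 7 | 71% | 1.4–1.7 | 2.3 → 3.4–3.6 | 23% → 22–24% |
| 8 | 93% | 0.4–0.7 | none | 42% → 48–52% |

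Most skips are from 200 to 400 mg (47% to 81% of trials). Skips from 400 to 600 or 700 mg occur in about 11% to 64%, and from 300 to 600 mg in under 1%. In scenario 3 about 0.9 of the rise in exposure is at 400 mg, where the true rate is 0.36.

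**Step 5: the two conclusions.** Safety: Table 3 minus Table 4 in scenarios 4 to 8 is 0.67, 0.71, 1.12, 0.00 and 0.82 points. Under the cap the gap to the printed 3+3 values is 1.4 to 3.1 points. In scenario 3 it is 19.7 − 19.26, about 0.4. Accuracy: in scenario 7 the cap selects 400 mg in 26–28% of trials and the true MTD, 500 mg, in 22–24%.

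**The case against.** The strongest reply is that the main comparison survives. Correct selection under the cap against the printed 3+3 value is 30–31% against 28.2%, 46–47% against 41.7%, 37–38% against 26.9%, 57–58% against 45.8%, 22–24% against 21.3% and 48–52% against 32.1% in scenarios 3 to 8. The cap does better in all six, and it improves on no-skip in scenarios 5, 6 and 8. This stands.

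Scenario 7 was already close. Table 3 has 0.233 against 0.204 on 1,000 trials. The standard error of the difference is √[(0.233 + 0.204 − 0.029²)/1000] = 0.021, so the lead is about 1.4 standard errors. The new leader, 400 mg, has a true DLT rate of 0.17, so the error is toward a lower dose. A shorter cap run of 3,000 trials gave 24.8% against 23.6%, within simulation error; another of 4,000 gave 28.5% against 23.1%. The direction is consistent, but the size is not firm.

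Some magnitudes are soft. The scenario 3 miss in step 3 (19.57 − 18.4, about 1.2 points) is nearly as large as the rise attributed to the cap there. A shorter scenario 8 run gave 55% correct selection, above the range shown.

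Skipping is also permitted, not prescribed. The model dose is a ceiling, observed DLTs and PK are weighed, and each escalation needs agreement between investigator and sponsor. Predicted median AUC (Table JBDA 7.1) rises only 3230/2620 − 1 = 23% from 200 to 400 mg and 3980/3230 − 1 = 23% from 400 to 700 mg. This makes the figures upper bounds. It does not remove the mismatch, because the simulations assumed a firm prohibition and the plan contains none.

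**Conclusion.** The concern holds. The simulated escalation is stricter than the written one from 200 mg BID upward, and overdose control does not close the gap. If the model dose is always taken up to the cap, 55% to 93% of trials in scenarios 3 to 8 skip a level. Mean percentage with a DLT rises by 0.4 to 1.9 points, and up to 1.5 more patients on average are treated above a 35% DLT rate (scenario 4). The safety statement is weakened but not overturned. The statement that the correct MTD is the most selected dose in every scenario does not hold in scenario 7 under the cap. The claim of better accuracy than 3+3 remains supported in scenarios 3 to 8.

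These results rest on the stated prior and stopping rules, the 50 mg convention when no dose qualifies, and full use of the model recommendation. The mismatch in the text depends on none of these. It should be corrected, but it does not invalidate the design.

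**What to change.** Choose one rule and use it throughout.

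1. **Adopt no skipping.** State in Protocol 6.2, 7.2.2.2, Attachment 10 section 1.2 and SAP 5.3.2 that escalation may not pass over a planned dose level that has not yet been given, with the 100% cap and the model ceiling still applying. Table 3 then stands. This takes one sentence in four places. With no DLTs, 700 mg is first reached in cohort 8 instead of cohort 5 or 6. In scenario 8 the cost is about 2 to 3 more patients on average, and 700 mg is selected in 42% of rerun trials instead of 48–52% (Table 3 prints 45.6%).
2. **Keep the cap alone.** Rerun Table 3 under it, restate the accuracy and safety conclusions, and add mean patients treated at a true DLT rate above 35% to the table. The cost is a simulation rerun and revised text, plus more patients above a 35% DLT rate if the curve is steep between 300 and 400 mg.
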